When the MMRM is used, the model will include treatment, geographic region, baseline CRP status, baseline value, visit, baseline value-by-visit, and treatment-by-visit interaction as fixed factors. The covariance structure to model the within-patient errors will be unstructured. If the unstructured covariance matrix results in a lack of convergence, the similar approach specified above for categorical MMRM will be used. The Kenward-Roger method will be used to estimate the denominator degrees of freedom. Type III tests for the least-squares (LS) means

will be used for the statistical comparison; the 95% CI will also be reported. Treatment group comparisons with placebo at Week 16 (Visit 8) and all other visits will be tested.

When the ANCOVA is used, the model will include treatment, geographic region, baseline CRP status and baseline value. Type III sums of squares for the LS means will be used for the statistical comparison; the 95% CI will also be reported.

The impact of ixekizumab starting dose of 160 mg versus 80 mg on time to onset (focus on Week 4) and treatment response during Period 2 (focus on Week 16) will be summarized and evaluated; details will be specified in the SAP.

For variables that are not collected at each postbaseline visit, data may exist at visits where the variable was not scheduled to be collected, due to early discontinuation visits. In these situations, data from the early discontinuation visit that do not correspond to the planned collection schedule will be excluded from the MMRM and categorical MMRM analyses. However, the data will still be used in other analyses, including shift analyses, change from baseline to last observation carried forward (LOCF) or modified baseline observation carried forward (mBOCF) endpoint analyses, and other categorical analyses.

Fisher's exact test will be used for all AE, baseline, discontinuation, and other categorical safety data. Continuous vital sign and laboratory values will be analyzed by an ANCOVA with treatment and baseline value in the model.

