Appendix

Page

3. Revision History

Statistical Analysis Plan (SAP) Version 1 was approved prior to first patient visit, on April 7, 2016.

Statistical Analysis Plan (SAP) Version 2 was approved prior to first unblinding, on January 19, 2018.

Statistical Analysis Plan (SAP) Version 3 was approved after unblinding.

Revisions since Version 1:

Section	Action
Section 4 Objectives	Updated per protocol amendment
Section 5	Clarified stratification factor
Section 6.1.1 General Considerations for Period 2	Revised geographic region in primary analysis model, clarified analysis for CRP, ASDAS disease states, removed ASDAS inactive disease, clinically important improvement, and ASDAS from starting dose analyses
Section 6.1.2 General Considerations for Period 3	Clarified baseline definition for TEAE for Period 3 per program safety analysis plan (PSAP) v8.0 language; added additional safety analyses for combined period 2 and 3
Section 6.2 Adjustment for Covariates	Updated geographic region
Section 6.3.5 Tipping Point Analysis	Updated methodology to 2-D analysis
Section 6.5 multiple comparison	Revised weights for graphical multiplicity testing procedure and order of 2 nd outcomes within tiers
Section 6.6 Patient disposition	Adding log-rank test for time to discontinuation
Section 6.7 Patient characteristics	Updated/clarified some baseline variables , adding spine SPARCC per protocol amendment
Section 6.7.2 Historical Illness and Preexisting Conditions	Updated analyses for pre-existing conditions for Period 2 and 3
Section 6.8 Treatment compliance	Updated population for treatment compliance analyses
Section 6.9.1 Previous Therapy	Removed Previous therapy due to redundancy to previous AxSpA therapy
Section 6.9.2 Concomitant therapy	Removed summary of concomitant therapy for PSFU period
Section 6.10 Efficacy analyses Table 6.4	updated calculation for BASMI tragus to wall distance; clarified how to handle 'non-evaluable' for MASES; added additional descriptions for TJC/SJC; updated MRI related scores per protocol amendment; updated analysis for anterior uveitis;
Section 6.10 Efficacy analyses Table 6.5	Updated analyses for MRI related scores per protocol amendment a; Added additional analyses for TJC/SJC; Updated language for anterior uveitis Revised analysis for ASDAS disease activity states Updated analysis population for enthesitis and TJC/SJC, ASAS-NSAID score
Section 6.10.2 Major Secondary Efficacy Analyses	Updated MRI score per protocol amendment a

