5.2. Method of Assignment to Treatment

Patients who meet all criteria for enrollment will be randomized to double-blind treatment at Week 0 (Visit 2). Assignment to treatment groups will be determined by a computer-generated random sequence using an interactive web-response system (IWRS). The IWRS will be used to assign double-blind investigational product to each patient. Site personnel will confirm that they have located the correct assigned investigational product package by entering a confirmation number found on the package into the IWRS.

To achieve between-group comparability, the randomization will be stratified by country and baseline CRP (nonelevated or elevated, elevated defined as >5.00 mg/L). Due to operational feasibility, stratification by CRP is based on the most recent CRP prior to randomization, i.e. screening CRP.

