the within-patient errors will be unstructured. The REML will be used. The Kenward-Roger method will be used to estimate the denominator degrees of freedom. Type III tests for the least-squares (LS) means will be used for the statistical comparison; the 95% CI will also be reported. Treatment group comparisons with placebo at Week 16 (Visit 8) and all other visits will be reported. If the unstructured covariance matrix results in a lack of convergence, the similar approach specified above for categorical MMRM will be used.

For the analysis of CRP, the MMRM model will include treatment, geographic region, baseline CRP status, visit, and treatment-by-visit interaction as fixed factors. Note for the ratio of postbaseline to baseline in CRP, analysis will be performed on the natural log transformed ratio.

When the ANCOVA is used, the model will include treatment, geographic region, baseline CRP status, and baseline value (except for the analysis of CRP, see paragraph below). Type III sums of squares for the LS means will be used for the statistical comparison; the 95% CI will also be reported.

For the analysis of CRP, the ANCOVA model will include treatment, geographic region, and baseline CRP status. Note for the ratio of postbaseline to baseline in CRP, analysis will be performed on the natural log transformed ratio.

For the analysis of ASDAS disease activity states (ie, inactive, moderate, high, and very high disease states), the repeated measures proportional odds model will include treatment, geographic region, baseline CRP status, visit, and treatment-by-visit interaction.

The impact of ixekizumab starting dose of 160 mg versus 80 mg on treatment response at Week 16 and time to onset of action will be summarized and evaluated. Response rates in categorical variables (including ASAS40, ASAS20, ASDAS major improvement) and LS mean change in continuous efficacy measures (including CRP, BASFI) at Week 16 will be presented for patients randomized to ixekizumab Q2W or Q4W treatment regimen with ixekizumab 160 mg starting dose and with ixekizumab 80 mg starting dose.

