For response rates, starting dose comparisons within ixekizumab Q2W or Q4W treatment regimens will be based on logistic regression model with treatment, starting dose, and treatment-by-starting-dose interaction (only ixekizumab Q2W and Q4W will be included in the analyses). Starting dose comparison combining ixekizumab Q2W and Q4W treatment regimens will be based on logistic regression model with only starting dose in the model.

For mean change analysis, starting dose comparisons within ixekizumab Q2W or Q4W treatment regimens will be based on MMRM model with treatment, starting dose, baseline value, visit, baseline value-by-visit, treatment-by-visit, treatment-by-starting dose, starting dose-by-visit, and treatment-by-starting dose-by-visit interactions as fixed factors. Starting dose comparison combining ixekizumab Q2W and Q4W treatment regimens will be based on MMRM model with starting dose, baseline value, visit, baseline value-by-visit, and starting dose-by-visit interaction as fixed factors. The differences in response rates and LS mean changes between starting doses and the corresponding 95% CI will be reported as well.

Time to onset analyses will focus on earlier time points (for example, Weeks 1, 2, 4, and so on) for abovementioned response variables in a similar fashion. For time to first clinical response analysis, starting dose comparisons within and across ixekizumab Q2W and Q4W treatment regimens will be based on log-rank test.

For variables that are not collected at each postbaseline visit, data may exist at visits where the variable was not scheduled to be collected, due to early discontinuation visits. In these situations, data from the early discontinuation visit that do not correspond to the planned collection schedule will be excluded from the MMRM and categorical MMRM analyses (Andersen and Millen 2013). However, the data will still be used in other analyses, including shift analyses, change from baseline to last-observation carried forward (LOCF) or modified baseline observation carried forward (mBOCF) endpoint analyses, and other categorical analyses.

For selective efficacy measures, percent improvement will be calculated as $100 \times (\text{baseline score} - \text{observed scores}) / \text{baseline score}$, unless specified otherwise. If a patient has experienced an improvement, this measure will be positive. If a patient has experienced a worsening, this measure will be negative.

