6.2. Adjustments for Covariates

The countries will be categorized into geographic regions for statistical analysis (Table RHBV.6.3). Unless otherwise specified, the statistical analysis models will adjust for

geographic region and baseline CRP status (nonelevated or elevated, elevated defined as >5.00mg/L).

Below are the country allocations.

Table RHBV.6.3. Geographic Regions for Statistical Analysis

Geographic Region	Country or Countries
Europe	Russia ^a , Czech Republic, Hungary, Poland, Germany, The Netherlands
Non-Europe	United States, Canada, Mexico, Japan, Korea, Taiwan

^a Russia is combined with European countries due to the small number of Russian patients and the preponderance of investigative sites in the western part of Russia.

In general, when an MMRM is to be used for analyses, baseline value and baseline-by-visit interactions will be included as covariates; when an ANCOVA is to be used for analyses, baseline value will be included as a covariate.

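### The CRP comparisons with placebo drop the baseline CRP value and keep only the two-level status, contrary to Protocol 9.2.1 and at a cost in precision

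*SAP*

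**What the plan says.** Protocol 9.2.1 gives one MMRM and one ANCOVA for continuous efficacy variables and makes no exception for CRP. For the MMRM, "the model will include treatment, geographic region, baseline CRP status, baseline value, visit, baseline value-by-visit, and treatment-by-visit interaction as fixed factors". For the ANCOVA: "When the ANCOVA is used, the model will include treatment, geographic region, baseline CRP status and baseline value".

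SAP 6.1.1 repeats those models but carves out CRP in both. For the MMRM: "For the analysis of CRP, the MMRM model will include treatment, geographic region, baseline CRP status, visit, and treatment-by-visit interaction as fixed factors". For the ANCOVA: "For the analysis of CRP, the ANCOVA model will include treatment, geographic region, and baseline CRP status". The outcomes analysed this way (SAP Table RHBV.6.5) are CRP change from baseline and the ratio of postbaseline to baseline CRP, the latter on the natural log scale.

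Two other parts of the SAP keep the baseline value. Section 6.2 states: "In general, when an MMRM is to be used for analyses, baseline value and baseline-by-visit interactions will be included as covariates". The starting-dose analysis in Section 6.1.1, which names CRP among its measures, uses an "MMRM model with starting dose, baseline value, visit, baseline value-by-visit, and starting dose-by-visit interaction as fixed factors" when the two regimens are combined; the within-regimen version also carries the baseline value.

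On the status factor, SAP 5.2 says that "stratification by CRP is based on the most recent CRP prior to randomization, i.e. screening CRP", whereas the analysis baseline in SAP 6.1.1 is the last value before the first injection, usually Week 0.

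**The concern.** Computing a change or a log ratio is not the same as adjusting for baseline. It subtracts the baseline value with a coefficient of exactly 1. If the true slope of postbaseline on baseline CRP within a status group is below 1, as one would expect when there is regression to the mean or a drug that lowers CRP, the subtraction over-corrects and leaves baseline noise in the outcome. Putting the baseline value in the model removes that noise. A two-level split at 5.00 mg/L removes only part of it.

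What is at stake is the width of the confidence intervals for CRP, and sensitivity to chance baseline imbalance within a status group. The exception is also unexplained: the revision history in SAP Section 3 says only that the CRP analysis was clarified. Finally, the SAP does not make clear whether the status in the model is the screening stratum or the Week 0 classification, and the screening stratum says less about the Week 0 value.

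**Working it through.** **The plan's own figure.** The documents give no figure for CRP. The only design figure is about 96% power for ASAS40 (44% v 16%, 80 per arm, two-sided Fisher's exact test at 0.05). Exact enumeration gives 96.7%, so it reproduces. This point does not touch it.

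**Assumptions for CRP.** No SD, median or correlation is given. Assumed: log-normal CRP, median 5 to 8 mg/L, SD of ln CRP 1.0 to 1.2 at both times, baseline to Week 16 correlation r on the log scale from 0.3 to 0.9. The calculation treats a single visit.

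**Log ratio, status taken from the Week 0 value.** In units of the ln CRP variance, post = r × baseline + error, with error variance 1 − r². So ln(post/baseline) = −(1 − r) × baseline + error. With V the share of ln-baseline variance left within status groups:

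- residual variance with status only: (1 − r²) + (1 − r)² V
- residual variance with ln(baseline) added: 1 − r²
- ratio: 1 + V(1 − r)/(1 + r)

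For a split at the median, V = 1 − 2/π = 0.363.

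| r | Variance ratio | SE increase | 80 per arm acts like |
|---|---|---|---|
| 0.3 | 1 + 0.363 × 0.7/1.3 = 1.196 | 9.3% | 66.9 |
| 0.5 | 1 + 0.363 × 0.5/1.5 = 1.121 | 5.9% | 71.4 |
| 0.7 | 1 + 0.363 × 0.3/1.7 = 1.064 | 3.2% | 75.2 |
| 0.8 | 1 + 0.363 × 0.2/1.8 = 1.040 | 2.0% | 76.9 |
| 0.9 | 1 + 0.363 × 0.1/1.9 = 1.019 | 1.0% | 78.5 |

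With the cut away from the median, V is larger (0.397 when 35% or 65% are elevated). Simulation over the whole assumed range gives variance inflation of 20% to 22% at r = 0.3, 12% to 14% at 0.5, 6% to 7% at 0.7, 4% to 5% at 0.8 and 2% at 0.9.

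**Two-arm check.** In 6,000 simulated trials of 80 v 80 (median 6.5, SD 1.1), the standard error without ln(baseline) was 9.3%, 5.8%, 3.0%, 1.7% and 0.7% larger at r = 0.3, 0.5, 0.7, 0.8 and 0.9, with no bias in either model. For an assumed 36% lower CRP, power without v with ln(baseline) was 68% v 75%, 79% v 84%, 94% v 95% and 99% v 99% at r = 0.3, 0.5, 0.7 and 0.8.

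**Log ratio, status taken from screening.** Assume screening correlates 0.8 to 0.9 with Week 0 and adds nothing about Week 16 once Week 0 is known. At a median split, V rises to 1 − 0.8² × 0.637 = 0.592 or 1 − 0.9² × 0.637 = 0.484. Across the assumed range the variance inflation is 9% to 34% at r 0.3 to 0.7 and 3% to 7% at 0.8 to 0.9.

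**Chance imbalance.** With 80 v 80, one standard error of within-status imbalance in ln baseline is SD × √V × √(2/80), about 0.10 to 0.12. The estimate shifts by (1 − r) times that: about 3% to 9% in the CRP ratio at r 0.3 to 0.7, and 1% to 2% at 0.8 to 0.9.

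**Untransformed change.** The loss is greater. Without a drug effect, simulated standard errors were about 12% to 29% larger at r 0.3 to 0.7. With an assumed 55% drug reduction in CRP (80 per arm, median 6 with SD 1.0 or median 8 with SD 1.2, either reading of status), they were 32% to 55% larger.

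**The case against.** The strongest case is that the exception is deliberate, was set before unblinding, and is allowed. The SAP flags it in both model descriptions. It is listed among the revisions since Version 1, Version 2 preceded unblinding, and the changes since Version 2 mention no CRP model. Protocol 9.2 requires an amendment only for a change to a principal feature and puts the justification for other changes in the study report, which is not among these documents. SAP 6.2 speaks only of a general rule. All of this stands: nothing suggests a data-driven choice, and a missing reason in the SAP is not itself a breach.

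The starting-dose models are also an imperfect comparison. They contain neither status nor region, so each CRP model could be read as carrying one baseline CRP term. That is fair, but the SAP does not state this rationale, and overlap between the two terms would not be a good reason for it. Two correlated baseline covariates do not harm a randomized treatment contrast. The SAP accepts the same overlap for ASDAS, whose model includes CRP status and a baseline score that itself contains ln(CRP + 1).

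The sizes rest on assumed correlations that the documents neither support nor exclude, and at high correlation the loss for the log ratio is trivial. This also stands. Which CRP the status comes from is a question for every model that uses the factor, so the screening-based figures should be read separately from the omitted covariate.

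**Conclusion.** The concern holds. SAP 6.1.1 removes the baseline CRP value from both CRP models, Protocol 9.2.1 includes it, and neither document explains why.

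The cost is precision, not systematic bias. Under the stated log-normal assumptions, confidence intervals for the log ratio are about 3% to 11% wider at correlations of 0.3 to 0.7 and 1% to 2% wider at 0.8 to 0.9. The loss is larger for untransformed change, and larger for the log ratio if status means the screening stratum. It would vanish only if the within-status slope on baseline were 1.

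The reach is limited. CRP change and ratio are other secondary outcomes without multiplicity control, so the primary and major secondary inference does not change. Adalimumab v placebo for CRP is affected in the same way as ixekizumab v placebo. The correction is worth making because it is cheap and restores the protocol's own model.

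**What to change.** - **Log ratio:** add ln(baseline CRP) and its interaction with visit to the MMRM, and ln(baseline CRP) to the ANCOVA.
- **Untransformed change:** add the baseline CRP value, with its visit interaction in the MMRM, as the SAP's general rule already provides.
- **Status:** keep CRP status as the stratification factor, and state in one sentence whether it is the screening or the Week 0 classification.
- **Reporting:** the SAP records that "Statistical Analysis Plan (SAP) Version 3 was approved after unblinding", so models added now should be reported as labelled additional analyses beside the planned ones, not in place of them. Give the reason for the CRP exception in the clinical study report, as Protocol 9.2 requires for changes to the described methods.

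The cost is one or two terms per model and a few lines of text. All the values are already collected.

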The effectiveness of ixekizumab in treating rad-axSpA will be assessed primarily by the ASAS40 response rate at Week 16. ASAS20 response will also be assessed at Week 16. These measures and the Week 16 endpoint are in alignment with efficacy endpoints for currently approved rad-axSpA therapies and with regulatory guidance (EMA 2009). Steady-state exposure of ixekizumab is expected to be reached by Week 16. Based on previous studies with ixekizumab in patients with psoriasis, RA, and PsA, it is anticipated that maximum or near

maximum clinical effect in rad-axSpA will be achieved within this timeframe for both ixekizumab treatment regimens as well as for the active control treatment group.

Baseline CRP has been reported as a predictor of response in patients with rad-axSpA treated with TNF inhibitors (Inman et al. 2008; de Vries et al. 2009; Sieper et al. 2011; Vastesaeger et al. 2011); hence by including it as a stratification factor, it ensures balance in baseline CRP levels resulting in greater comparability across treatment groups at baseline.

The Extended Treatment Period (Period 3) will permit collection of data for the assessments of maintenance of efficacy and long term safety with ixekizumab.

The Post-Treatment Follow-Up Period (Period 4) is important for safety and efficacy monitoring following administration of the last study treatment.

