As a secondary analysis for the primary and major secondary categorical efficacy measures, a categorical mixed-effects model of repeated measures (categorical MMRM) estimating the percentage of patients achieving response across postbaseline visits may be used. The model will include treatment, geographic region, baseline CRP status, visit, treatment-by-visit as fixed factors, as well as the continuous, fixed covariate of baseline value and baseline value-by-visit interaction (when appropriate). The binomial distribution and the logit link will be used. An unstructured covariance matrix will be used to model the within-patient variance-covariance errors. The Kenward-Roger approximation will be used to estimate the denominator degrees of freedom. The Newton-Raphson with ridging optimization technique will be used to aid with convergence. The probability of response, the corresponding 2-sided 95% CI, and the p-value for treatment comparisons at Week 16 (Visit 8) and all other postbaseline visits will be reported.

If the unstructured covariance matrix results in a lack of convergence, the heterogeneous Toeplitz covariance structure, followed by the heterogeneous autoregressive covariance structure, followed by the compound symmetry, will be used. This order is specified according to a decreasing number of covariance parameters in the structure. The sandwich estimator (Diggle et al. 1994) for the covariance estimation will be used by specifying the EMPIRICAL option in SAS PROC MIXED. When sandwich estimation is used, the Kenward-Roger approximation for denominator degrees of freedom cannot be used. Instead, the DDFM=BETWITHIN option will be used to estimate denominator degrees of freedom.

The primary analyses for continuous efficacy and health outcomes variables will be made using MMRM. A secondary analysis for continuous efficacy and health outcomes variables will be made using analysis of covariance (ANCOVA).

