ASDAS	ASDAS Disease Activity States	Repeated measures proportional odds model analysis with NRI	ITT Population	IXE80Q2W & IXE80Q4W vs. placebo at all other postbaseline visits in Period 2	Other secondary efficacy analyses for primary outcome (Section 6.10.4)
		Descriptive statistics of ASDAS disease activity states	Extended Treatment Period Population	No treatment group comparisons during Period 3	Other secondary efficacy analyses (Section 6.10.4)
ASDAS	ASDAS clinical important improvement; major improvement	Logistic regression analysis with NRI; Fisher's exact test with NRI	ITT Population	IXE80Q2W & IXE80Q4W vs. placebo at Week 16 and all other postbaseline visits in Period 2	Other secondary efficacy analyses (Section 6.10.4).
		KM analysis of time to first Response	ITT Population	IXE80Q2W & IXE80Q4W vs. placebo during Period 2	Other secondary efficacy analyses (Section 6.10.4).
		Logistic regression analysis with NRI	ITT Population	IXE80Q2W & IXE80Q4W Starting Dose 160 mg and 80 mg during Period 2 for ASDAS major improvement	Other secondary efficacy analyses (Section 6.10.4).

Measure	Variable	Analysis Method (Sections 6.1, 6.3)	Population (Section 6.1.5)	Comparison/Time Point	Analysis Type
		Descriptive statistics of response rate	Extended Treatment Period Population	No treatment group comparisons during Period 3	Other secondary efficacy analyses (Section 6.10.4).
		Descriptive statistics of response rate	ITT Population Who are Initially Randomized to Ixekizumab	No treatment group comparisons during Combined Periods 2 and 3	Other secondary efficacy analyses (Section 6.10.4).
BASDAI	BASDAI50 – Major Secondary	Logistic regression analysis with NRI	ITT Population	IXE80Q2W & IXE80Q4W vs. placebo at Week 16	Major secondary efficacy analysis is logistic regression analysis with NRI for ITT Population comparing IXE80Q2W & IXE80Q4W vs. placebo at Week 16 (Section 6.10.2).
		Logistic regression analysis with NRI	ITT Population	IXE80Q2W & IXE80Q4W vs. placebo at all other postbaseline visits in Period 2	Other secondary efficacy analyses (Section 6.10.4).
		Categorical MMRM	ITT Population	IXE80Q2W & IXE80Q4W vs. placebo at Week 16 and all other postbaseline visits in Period 2	Other secondary efficacy analyses (Section 6.10.4).
		Fisher’s exact test with NRI	ITT Population	IXE80Q2W & IXE80Q4W vs. placebo at Week 16 and all other postbaseline visits in Period 2	Other secondary efficacy analyses (Section 6.10.4).

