6.10.2. Major Secondary Efficacy Analyses

The major secondary outcomes at Week 16 (Visit 8) are:

- Proportion of patients achieving an ASAS20 response
- Change from baseline in ASDAS
- Proportion of patients achieving BASDAI50 response
- Change from baseline in BASFI
- Proportion of patients achieving ASDAS inactive disease
- Change from baseline in MRI SPARCC spine score
- Change from baseline in SF-36 PCS*
- Change from baseline in ASAS-HI*

* Detailed descriptions and analyses on SF-36 PCS and ASAS-HI are described in Table RHBV.6.6 and Table RHBV.6.7.

The major secondary analysis will be based on the ITT Population for Period 2 comparing each ixekizumab treatment group and placebo at Week 16 (Visit 8). In the major secondary analyses, treatment groups of ixekizumab 80 mg Q2W and Q4W will be analyzed without regard to starting dose.

The primary analysis for categorical major secondary outcomes is a logistic regression analysis with treatment, geographic region, and baseline CRP status in the model (Section 6.1.1). Missing data will be imputed using the NRI method (Section 6.3.1).

The primary analysis for continuous major secondary outcomes (except MRI SPARCC spine score) is an MMRM analysis with treatment, geographic region, baseline CRP status, baseline value, visit, baseline value-by-visit, and treatment-by-visit interaction as fixed factors (Section 6.1.1).

The primary analysis for change from baseline in MRI SPARCC spine score is an observed case analysis using ANCOVA with treatment, geographic region, baseline CRP status and baseline value in the model (Section 6.1.1). Only patients with both baseline and Week 16 SPARCC spine score will be included in the analysis.

These major secondary comparisons will be tested based on the graphical multiple testing procedure detailed in Section 6.5.

Table RHBV.6.5 provides the detailed analyses including analysis type, method and imputation, population, time point, and treatment comparisons for major secondary outcomes.

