6.10.4. Other Secondary Efficacy Analyses

There will be no adjustment for multiple comparisons for other secondary efficacy analyses.

The other secondary efficacy variables for secondary objectives include:

- ASAS40: analyses other than primary analysis (Section 6.10.1) and additional analysis of the primary outcome (Section 6.10.3)
- ASAS20: analyses other than major secondary efficacy analysis (Section 6.10.2)
- ASAS5/6 and partial remission
- ASDAS<2.1: ad hoc analysis post interim 1 database lock
- Change from baseline in individual components of the ASAS criteria (patient global, spinal pain, function [see BASFI below], inflammation [see BASDAI below], CRP [see CRP below], and spinal mobility (lateral spinal flexion) [see BASMI below])
- Change from baseline in BASDAI and inflammation (mean of Q5 and Q6 on BASDAI)
- BASDAI 50: analyses other than major secondary efficacy analysis (Section 6.10.2)
- Change from baseline in ASDAS: analyses other than major secondary efficacy analysis (Section 6.10.2)
- ASDAS inactive disease: analyses other than major secondary efficacy analysis (Section 6.10.2)
- ASDAS disease activity states: inactive disease, low disease activity, high disease activity, very high disease activity; clinically important improvement and major improvement
- Change from baseline in CRP
- Change from baseline in BASFI: analyses other than major secondary efficacy analysis (Section 6.10.2)
- Change from baseline in mobility (BASMI linear and individual components, chest expansion, occiput to wall distance)
- Change from baseline in MRI SPARCC spine score: analyses other than major secondary efficacy analysis (Section 6.10.2)
- Change from baseline in MRI SPARCC SIJ structural score (SSS) for each of the 4 features: fat metaplasia, bone erosion, backfill and ankylosis.
- Change from baseline in MRI ASSpiMRI –Berlin score
- Change from baseline in MRI SPARCC SIJ score
- Change from baseline in enthesitis score (MASES and SPARCC)
- Change from baseline in TJC and SJC scores
- Incidence of peripheral arthritis by TJC and SJC scores of 46/44 joints.
- Incidence rate of anterior uveitis or uveitis flares
- Change from baseline in ASAS-NSAID score (apply to Period 3 analysis only), Section 6.10.4.1.

Treatment comparisons of each ixekizumab treatment group and placebo, as well as adalimumab treatment group and placebo at Week 16 (Visit 8) and all other postbaseline visits during Period 2 will be provided.

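### The repeated measures proportional odds model for ASDAS disease states leaves out baseline ASDAS, which costs power in one supportive analysis

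*SAP*

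**What the plan says.** SAP 6.1.1 lists the terms for this analysis: "the repeated measures proportional odds model will include treatment, geographic region, baseline CRP status, visit, and treatment-by-visit interaction". Neither the baseline ASDAS score nor the baseline ASDAS state is among them. Table RHBV.6.5 describes the method as "Repeated measures proportional odds model analysis with NRI", in the ITT Population, for each ixekizumab regimen against placebo in Period 2. Table RHBV.6.4 defines the four states by absolute cut-points on the score (1.3, 2.1 and 3.5) and assigns the worst state when the score is missing.

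For change in ASDAS, a major secondary outcome, SAP 6.10.2 specifies an "MMRM analysis with treatment, geographic region, baseline CRP status, baseline value, visit, baseline value-by-visit, and treatment-by-visit interaction as fixed factors".

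The covariate rule in SAP 6.2 reads: "In general, when an MMRM is to be used for analyses, baseline value and baseline-by-visit interactions will be included as covariates". It makes a parallel statement for ANCOVA and none for proportional odds models.

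On multiplicity, SAP 6.10.4 says: "There will be no adjustment for multiple comparisons for other secondary efficacy analyses".

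**The concern.** The outcome is where a patient stands on the ASDAS scale, not how far the patient has moved. ASAS40, ASAS20 and BASDAI50 are defined relative to the patient's own starting values, so part of the baseline is already in the response. A disease state has no such reference. To leave the very high state, a patient who starts at 3.6 must fall by 3.6 − 3.5 = 0.1, and one who starts at 5.0 must fall by 5.0 − 3.5 = 1.5. A model without baseline ASDAS treats these two patients alike if their region and CRP status match.

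Baseline CRP status carries some of this information. But CRP is one of five ASDAS components, and status is a cut at 5 mg/L. Back pain, patient global, peripheral pain/swelling and duration of morning stiffness are not represented. Randomisation is stratified by country and CRP status only, so the design does not otherwise balance baseline ASDAS.

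At stake is the power of one other secondary analysis.

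**Working it through.** **1. The plan's own figure.** The documents give no power or effect size for this model. Their only power figure is about 96% for ASAS40 (80 per arm, 44% against 16%, two-sided Fisher's exact test at 0.05). Exact enumeration gives 96.7%, so the figure reproduces, but it has no bearing on the ASDAS-state model.

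**2. How the plan treats baseline value in related models.**

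| Analysis | Outcome | Baseline value in model? |
|---|---|---|
| MMRM of ASDAS change (SAP 6.10.2) | continuous | yes, with its visit interaction |
| ASDAS disease states (SAP 6.1.1) | four ordered levels | no |
| Categorical MMRM (SAP 6.1.1) | repeated binary | no |
| Logistic regression, including ASDAS inactive disease (SAP 6.1.1, 6.10.2) | binary | no |
| Categorical MMRM (Protocol 9.2.1; primary and major secondary measures) | repeated binary | yes where appropriate, with its visit interaction |

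The SAP adjusts ASDAS for baseline when it is analysed as a change and not when it is analysed as a state.

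**3. Simulation of the cost.** From the documents: 80 patients per arm and cut-points 1.3, 2.1 and 3.5. Assumed, with no source in the documents: baseline ASDAS mean 3.7 and SD 0.8; Week 16 placebo mean 3.2 and SD 1.0; treatment difference 0.5; 60% with elevated CRP; latent correlation 0.6 between CRP status and baseline ASDAS; baseline-to-Week-16 correlation r of 0.3, 0.5 or 0.7.

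With z, e and e′ independent standard normal:
- baseline = 3.7 + 0.8z
- Week 16 score = 3.2 − 0.5·treatment + 1.0·(r·z + √(1 − r²)·e)
- CRP elevated if 0.6z + 0.8e′ > −0.253

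Two proportional odds models were fitted to each simulated trial: treatment and CRP status, and the same plus continuous baseline ASDAS. Relative efficiency = [(mean adjusted log OR ÷ mean adjusted SE) ÷ (mean unadjusted log OR ÷ mean unadjusted SE)]².

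| r | Power without | Power with | Log OR without | Log OR with | Relative efficiency |
|---|---|---|---|---|---|
| 0.3 | 79.8% | 81.7% | −0.87 | −0.91 | 1.06 |
| 0.5 | 81.5% | 88.5% | −0.88 | −1.00 | 1.20 |
| 0.7 | 84.7% | 95.2% | −0.92 | −1.25 | 1.49 |

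The power gains are 1.9, 7.0 and 10.5 points (600 trials per row). The Monte Carlo SE of one power estimate is about √(0.8 × 0.2 / 600) = 1.6 points, so the gain at r = 0.3 is small. In patients, matching the adjusted model would take about 80 × 1.06 = 85, 80 × 1.20 = 96 and 80 × 1.49 = 119 per arm.

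**4. Validity.** With no treatment effect (500 trials per row), the model without baseline ASDAS rejected in 5.0%, 4.8% and 4.8% of trials, and the model with it in 5.4%, 6.4% and 3.6%. The Monte Carlo SE is √(0.05 × 0.95 / 500) ≈ 1.0 point, so all are compatible with 5%.

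**5. Where the gain comes from.** A separate run of 150 trials per scenario, also with CRP status in both models and all inputs assumed, gave these means:
- r = 0.3: SE 0.312 to 0.317, log OR −0.88 to −0.91; z ratio (0.91/0.317) ÷ (0.88/0.312) = 1.02.
- r = 0.6: SE 0.313 to 0.334, log OR −0.89 to −1.08; z ratio (1.08/0.334) ÷ (0.89/0.313) = 1.14.

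The SE rises slightly, but the coefficient moves further from zero. The benefit is power, not a narrower interval for the log odds ratio.

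**The case against.** The strongest reply is that the model follows the SAP's convention: baseline value for continuous outcomes, none for categorical ones. That stands as a description. The categorical MMRM has the same terms, and the logistic model for ASDAS inactive disease, itself a cut of the ASDAS level, also omits baseline ASDAS. A reader might infer that this model is the lone exception among the SAP's repeated-measures models; it is not. Nor does it breach SAP 6.2, whose rule is general and covers MMRM and ANCOVA only. Protocol 9.2.1 allows baseline value in a repeated categorical model, but for primary and major secondary measures, which disease states are not. Convention explains the omission; it does not recover the power.

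Two stronger readings are tempting. One is that the plan discards the strongest predictor of the outcome. Neither document ranks predictors of ASDAS state. The predictor of response that the protocol names is CRP ("Baseline CRP has been reported as a predictor of response in patients with rad-axSpA treated with TNF inhibitors"), and its status is in the model. The other is that omitting baseline ASDAS biases the treatment odds ratio. A chance imbalance can move one trial's estimate, but under randomisation there is no systematic bias, and simulated type I error stayed near 5%. The difference between the two log odds ratios reflects different estimands, not confounding.

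It is also fair that the size rests on an assumed correlation and a single visit, without the repeated-measures structure, region or the worst-state rule for missing scores. The range is therefore indicative.

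**Conclusion.** The point holds as a minor one. The ASDAS-state model leaves out a baseline score that the trial already derives and that bears directly on an outcome defined by absolute level. Baseline CRP status replaces it only in part. The test is valid; the cost is power. The relative efficiency of adding baseline ASDAS is about 1.06, 1.20 and 1.49 at correlations of 0.3, 0.5 and 0.7, under the assumptions listed, and the documents do not say where in that range the trial lies. Nothing in the alpha-controlled family depends on this model, and the major secondary analysis of ASDAS change already adjusts for baseline. The primary and major secondary conclusions are unaffected.

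**What to change.** Add continuous baseline ASDAS and baseline ASDAS-by-visit to the proportional odds model for disease states in SAP 6.1.1.

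No new data are needed: baseline ASDAS is already summarised under SAP 6.7.1. The change is one line of specification and one further model fit. There are two small downsides:
- The odds ratio becomes conditional on baseline ASDAS. Its size should not be compared with the unadjusted one, and the report should say so.
- SAP Version 3 was approved after unblinding, and its list of changes since Version 2 does not mention this model. The adjusted model should therefore be labelled supportive and shown beside the specified model, not put in its place.
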